## **10. ANALYSIS**

### **Timing of Analysis**

The primary analysis is based on outcomes at discharge. Secondary outcomes include outcomes at 3 months and 18 months. The main analysis will proceed after all units have crossed over to the study group for 30-days, and have contributed 3 months of follow up time, i.e. four months after the last unit begins intervention. Secondary analyses focused on 18-month outcomes will occur after 18 full months of follow up, i.e. at least 19 months after the last unit cross-over to the intervention condition.

### **Blinding**

There is no blinding in this study.

### **Descriptive analysis**

Initial analysis will be descriptive in nature. First, we will describe the flow of participants into the study and allocated to the two arms using a CONSORT diagram. Then, the study participants will be characterized based on demographic and clinical variables measured at the time of eligibility, unless otherwise indicated. Variables will be described using median and interquartile range or using count and percent (proportion). No statistical testing will be done to compare characteristics between groups. The following variables will be described by study arm and overall:

- Age (years)- Date of presentation-birthdate in years
- Race (categories same as for Clinical Trials.gov reporting: American Indian/Alaska Native, Asian, Native Hawaiian or Pacific Islander, Black or African American, White, More Than One Race, Unknown or Not Reported)- patient self-reported in EHR
- Ethnicity (Hispanic or Latino, Not Hispanic or Latino, Unknown or not reported)- patient self-reported in EHR

- Sex (Male or female, other, unknown)- patient self-reported in EHR
- Charlson comorbidity index
- Health literacy score- VUMC instruments- standard of care to collect for inpatients
- Unit admitted to at the time of study inclusion- first study unit on which patient spends at least 24 hours during the admission.
  - Unit on which challenge was performed- For those who received amoxicillin challenge, unit on which the testing was done.
- Penicillin allergy listed under allergies/problem list on day of admission
  - Proportion reporting allergy to any of the following indicated in Allergy field in eStar:
    - Ampicillin
    - Ampicillin/sulbactam (unasyn)
    - Amoxicillin
    - Amoxicillin/Clavulanate (augmentin)
    - Cloxacillin
    - Dicloxacillin
    - Nafcillin
    - Penicillin G
    - Penicillin VK
    - Piperacillin
    - Piperacillin/Tazobactam
    - Ticarcillin
    - Ticarcillin/Clavulanate (timentin)

Next, we will describe the fidelity of applying the intervention as follows:

- Penicillin allergy labeled patient completed risk assessment (as n (proportion) of total Penicillin Allergy Labels (PALs)
  - Highest- as n (proportion of risk assessed)
  - Higher- as n (proportion of risk assessed)
  - Low-risk allergy- as n (proportion of risk assessed)
- Patient received amoxicillin challenge as n (proportion of total PALs)
  - After qualifying as low-risk -as n (proportion of low-risk PALs)
- For each participant, duration of exposure to control environment versus intervention environment.

## Main Analysis

Prior to modeling the data, we will describe the presentation of the amoxicillin challenge, the response, any adverse events, the rate of penicillin allergy removal, and subsequent use of penicillin as follows:

- Patient response to amoxicillin challenge -as n (proportion of total PALs)
  - Pass/Fail
    - as n (proportion) of total challenges done

- Proportion of failed challenges in which hypotension was present
    - as n (proportion) of challenges failed
      - Hypotension defined as systolic blood pressure decrease of 30% compared to pre-challenge blood pressure.
- Patient allergy removed from the chart's allergy box- absent at discharge
  - as n (proportion of total PALs)
- Same hospitalization use of a penicillin antibiotic,
  - as n (proportion of total PALs)
- Adverse events associated with amoxicillin challenge,
  - as n (proportion) of total challenges
- Adverse events associated with same hospitalization use of a penicillin antibiotic
  - as n (proportion of total PALs),
- Allergy evaluation information present/absent in discharge summary,
  - as n (proportion of completed PALs assessed as low-risk)
- Number of subsequent VUMC healthcare encounters after the initial hospitalization
  - Outpatient
    - average n per patient
  - ED/observation
    - average n per patient
  - Hospitalization/Inpatient
    - average n per patient
  - Surgical
    - average n per patient
- Ratio of penicillin treatments per total patient healthcare encounters since study entry

**Primary model:** Penicillin allergy label removal will be compared between the two groups using an adjusted logistic regression mixed effects model. In addition to study group assignment, the model will be adjusted for the following baseline covariates: time from start of study, age, race/ethnicity, sex, comorbidity index, health literacy, and intervention unit as a random effect. We will additionally include intervention unit general acuity level, defined based on the average APRDRG for patients discharged from the unit during the study period. The magnitude of effect will be reported as odds ratios with confidence intervals. A critical two-sided p-value of 0.05 will be used to draw conclusions on the main effect of intervention.

**Subgroup analysis:** We do not have evidence suggesting subgroups will respond differently to the intervention. However, such a possibility does exist. Differential treatment effect will be analyzed as detailed in <https://hbiostat.org/bbr/ancova.html#strategy-for-analyzing-differential-treatment-effect>. Briefly, the analysis will avoid subgroup analysis because it does not properly handle continuous baseline variables such as age, and because it does not inherit covariate adjustment. Each factor that potentially interacts with treatment will have its treatment interactions added to the model, one interacting factor at a time. Continuous interacting baseline factors will be modeled as restricted cubic splines with 3 default knots so as to not assume linearity. For each analysis a plot will be made with the baseline factor in question on the x-axis and the estimated treatment effect and its 0.95 confidence band on the y-axis, accompanied by a statistical test for non-flatness of the curve (lack of interaction). The same analysis will be used to construct a model-based forest plot where for

continuous interacting factors, treatment effects will be estimated at quartiles of interacting factors (or discrete levels for categorical factors), neither of which involves stratifying/subgrouping the data.

**Sensitivity analysis:** We will repeat the main analysis without covariate adjustment. In the presence of missing outcomes, a sensitivity analysis using multiple imputation for missing outcomes may be conducted.

**Multiplicity:** This study is designed with a single primary endpoint and no interim analyses. Therefore, no adjustments for multiple testing will be made. Secondary analyses will emphasize effect sizes over statistical significance.

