## 1.0 Background

Up to 20% of the US population carries a label of penicillin allergy, the most commonly reported medication allergy. However, in the presence of appropriate skin and oral challenge testing in current practice only 4% or less of these allergy labels can be verified as accurate. Because most patients reporting allergy to penicillin aren't actually allergic their reported allergy leads to unnecessary avoidance of penicillins, treatment with less effective 2nd and 3rd line antibiotics with more side effects, and worsened outcomes. At Vanderbilt, in current practice, only 13.4% of patients ever get their penicillin allergy label removed, despite up to 96% being potentially able to tolerate a penicillin safely.

When asked about their history of penicillin allergy, most patients report symptoms that are considered low-risk by specialists in allergy. Low-risk penicillin allergies are routinely challenged by allergy doctors with test dose challenges, meaning a small dose of amoxicillin is given and the patient is observed. Patients who tolerate the medication during observation have their allergy label to penicillin removed from the chart. Test dose challenges are known to be safe in low-risk patients and are recommended as a tool in penicillin allergy evaluation by the American Academy of Asthma, Allergy and Immunology. Unfortunately, test dose challenges are not performed as a part of routine practice outside of the field of allergy due to most physicians being unfamiliar with the features of low-risk penicillin allergy and the procedure of performing a test dose challenge.

Therefore, we developed a risk stratification tool validated on the outcomes of penicillin allergy testing in the Vanderbilt Drug Allergy Clinic that can help physicians to identify low-risk penicillin allergy patients who would successfully tolerate a test dose challenge.

Our objective is to increase the familiarity with penicillin allergy history taking among physicians, and the rate at which low-risk penicillin allergies are tested and removed in current practice.

We plan to perform a stepped wedge cluster randomized trial of this best practices intervention to provide risk stratification and test dose amoxicillin challenges in patients who are at low risk of having an ongoing penicillin allergy, using our internally validated risk stratification tool.

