## 1. INTRODUCTION

This document describes the statistical analysis plan (SAP) for a single center, stepped wedge, randomized, pragmatic, clinical trial of an intervention to remove low risk penicillin allergy labels using a single dose amoxicillin challenge. The intervention is deployed at the medical unit level, led by a unit pharmacist. Persons on the unit with a penicillin allergy label undergo a risk assessment, and low risk patients who consent to the procedure are presented with an oral amoxicillin challenge.

At the study outset, all participating units were naïve to the process for removing penicillin allergies. After the run-in period, medical units transitioned from the control condition to the intervention condition at monthly intervals. Medical units at VUMC will be randomized to determine the order in which they start the intervention.

This SAP describes the approach to analyzing the primary and secondary endpoints, as well as safety endpoints, once the trial is stopped.

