## 8. DESIGN CONSIDERATIONS

### Randomization

During the trial, randomization will occur at the level of the medical unit. A single medical unit will serve as a cluster. Twelve medical units were selected for inclusion, and the order of starting the intervention was randomized, staggered by one-month intervals.

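### The primary model assumes one constant effect from go-live, so if uptake ramps up or fades the reported odds ratio is biased, although the test of any effect is almost unaffected

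*SAP*

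**What the plan says.** SAP section 10, Main Analysis, states: "Penicillin allergy label removal will be compared between the two groups using an adjusted logistic regression mixed effects model". It continues: "In addition to study group assignment, the model will be adjusted for the following baseline covariates: time from start of study, age", followed by other patient covariates, a random effect for unit and a unit acuity measure. On reporting: "The magnitude of effect will be reported as odds ratios with confidence intervals". On inference: "A critical two-sided p-value of 0.05 will be used to draw conclusions on the main effect of intervention". Whether calendar time is linear or categorical is not stated.

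The design is in SAP section 8, Randomization: "Twelve medical units were selected for inclusion, and the order of starting the intervention was randomized, staggered by one-month intervals". SAP section 1 adds: "At the study outset, all participating units were naïve to the process for removing penicillin allergies".

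Several other provisions come near the point without covering it:

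- The 24-hour rule in SAP section 2, and the exposure duration under Descriptive analysis, concern individual patients. Neither concerns how long a unit has been live.
- The Subgroup analysis paragraph allows treatment interactions one factor at a time. It names no such factor, and its modelling is described for baseline factors.
- The sensitivity analyses are a repeat without covariate adjustment and possible imputation of missing outcomes.

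**The concern.** In a stepped wedge, months since go-live rise with calendar time. A model with a single step at go-live has nowhere to put a change in uptake that develops after the step, except partly in the calendar term. Normally the control periods anchor that term. Here removals under control are so rare that they anchor it very weakly. A ramp-up on live units is then read partly as a secular rise and projected back onto controls, which shrinks the intervention coefficient. Fading does the reverse.

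A ramp-up is plausible because the units began with no experience of the process. What is at stake is the size of the reported odds ratio and the coverage of its interval. At the planned effect a significant result is nearly assured, so the size of the effect is most of what the trial adds.

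**Working it through.** **The plan's own figure.** The plan gives no figure for this point. Its 35 per group comes from an individually randomised comparison of two proportions (pooled, two-sided, 80% power). That test gives 36 for 0.5% against 20.5% and 35 for 0.1% against 20.1%. It contains neither units nor time and does not bear on the question.

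**Step 1: layout.** Inputs from SAP section 8 are 12 units, one-month steps, 10 to 15 labelled patients per unit-month and 0.5% removal under control. Take the first unit live in month 1.

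- Live unit-months: 12 + 11 + ... + 1 = 78. Control unit-months: 144 − 78 = 66.
- Expected control removals: 66 × 10 × 0.005 = 3.3 to 66 × 15 × 0.005 = 5.0.
- Share of live unit-months in a unit's first three live months: (12 + 11 + 10)/78 = 42%. In months 7 to 12: (6 + 5 + ... + 1)/78 = 27%.

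**Step 2: true averages under an assumed curve.** Take 5% uptake in month 1, rising linearly to 20.5% in month 6 and then flat.

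- The monthly odds ratio runs from (0.05/0.95)/(0.005/0.995) = 10.5 to (0.205/0.795)/(0.005/0.995) = 51.3.
- The average log odds ratio weighted by patients (weights 12, 11, ..., 1) is 3.379, an odds ratio of 29.4. Weighted equally by month it is 3.603, or 36.7.
- The odds ratio of the average risk is 32.8 by patients and 39.7 by months.
- Any sensible average therefore lies between 29 and 40.

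**Step 3: what the planned model returns.** Random-intercept logistic fits by Gauss-Hermite quadrature used a group indicator and linear calendar time, with 12 patients per unit-month. Assumptions not in the documents are the curves, a unit SD of 0.3 on the logit scale and no true secular trend. Odds ratios are large-sample. Coverage comes from 150 single trials per pattern, against the patient-weighted and the equal-month average log odds ratio.

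| Uptake by month since go-live | True averages | Planned model | 95% interval coverage, patient / month average |
|---|---|---|---|
| Constant 20.5% | 51 | 52 | 97% / 97% |
| 5% to 20.5% by month 3, then flat | 37 to 45 | 26 | 89% / 79% |
| 5% to 20.5% by month 6, then flat | 29 to 40 | 15 | 78% / 66% |
| 20.5% to 5% by month 6, then flat | 17 to 26 | 81 to 82 | 37% / 18% |

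In the fading case the estimate exceeds the largest monthly odds ratio, 51. The test still rejects in 97% to 99% of trials under the three changing patterns.

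**Step 4: form of calendar time.** Calendar month as a factor gives nearly the same answer. In a logistic check without unit effects, using steeper assumed curves, factor against linear time gave 17.0 against 16.6 (uptake 5% rising to 35% over 12 months) and 85.5 against 85.7 (35% falling to 10%). The true averages there were 22.7 to 33.5 and 48.7 to 63.3.

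**Step 5: percentage points, for patients on live units.**

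- Steep 12-month patterns: about 9 against a true 11.2 (rising) and about 27 against 24.5 (falling), errors of about 2 to 3 points.
- Milder ramps from 5% to 20.5%, flat from month 4 or from month 7: 14.6 against 15.5 and 11.7 against 12.8, errors of about 1 point.
- The choice of average matters as much. Under the steep patterns the true gain averaged equally over live months is 16.2 (rising) and 20.3 (falling), which differs from the patient average by 5.0 and 4.2 points.

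**Step 6: does an exposure-time model recover the truth?** With a separate effect for each month since go-live, the large-sample patient-weighted odds ratios are 37.1, 29.9 and 22.1 for the three changing patterns (true 37.1, 29.4, 22.0). At single-trial size, four bins (month 1, 2–3, 4–6, 7–12) give 95% to 97% coverage of the patient-weighted average. The median under fading is 25.4 against 22.0, so some small-sample error remains.

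**The case against.** The strongest reply is that the trial's stated question is whether the intervention removes more labels than usual care, and the planned test answers it. That stands.

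The curves are also assumed. The SAP describes a pharmacist-led process with systematic identification of labelled patients, which might run at a steady level from the first month. The protocol's wording, "Our objective is to increase the familiarity with penicillin allergy history taking among physicians", states an aim and does not predict rising uptake. That stands too, so a ramp-up is plausible but not established.

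Existing analyses give partial protection. If the unadjusted repeat drops calendar time, it comes close to the patient-weighted odds ratio under ramp-up (37.7 against 37.1; 29.0 against 29.4). It does not under fading (30.6 against 22.0), and it gives up protection against a real secular trend. A large gap between adjusted and unadjusted results would be a warning, not a remedy. A treatment-by-calendar-time interaction could be read into the Subgroup paragraph. It would be wrong to say the plan can show nothing about growth or fading, but calendar time is not months since go-live.

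Two stronger readings are tempting. One is that the model misstates the gain by enough to reverse success or failure on 20 additional removals per 100. No section makes 20 points a success criterion; it is a sample-size assumption. The other is that the gain is wrong by 4 to 6 points: 7.1 against 11.2 and 30.9 against 24.5 under the steep patterns. Those comparisons set a model figure standardised over all patients, controls included, against a truth for live-unit patients only. Compared on the same patients, the error is the 2 to 3 points in step 5.

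**Conclusion.** The point holds for effect size only. If uptake changes with months since go-live, part of the change is taken up by the calendar term. The reported odds ratio is then too low under ramp-up and too high under fading, by roughly a factor of two or more for the six-month patterns, and its interval under-covers. If uptake is constant there is no bias. The test of any effect is almost unaffected, and the error in percentage points for live-unit patients is modest.

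The direction rests on the design and the near-absence of control removals, both taken from the SAP. The sizes rest on assumed curves, an assumed unit SD and no true secular trend, so they are illustrations and not forecasts. The plan also does not say which average its odds ratio is meant to estimate when the effect varies. Cheap improvement.

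**What to change.** Keep the primary model and its test as planned, and state the form of calendar time. Then add to the SAP:

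- **A companion model** with the same covariates, the unit random effect and calendar time, in which the single group term is replaced by a flexible effect of months since the unit's go-live, zero under control. Bins such as month 1, 2–3, 4–6 and 7–12, or a spline, would serve. A single linear term is not enough. For a ramp that is flat from month 4, the true equal-month gain is (5 + 10.17 + 15.33 + 9 × 20.5)/12 − 0.5 = 17.4 points, and a linear term returned about 19.
- **A target average fixed in advance**, for example over patients on live units, reported with its interval whether or not the exposure-time term is significant. Switching the quoted effect on the result of that test would be data-driven selection.
- **A table** of removal by month since go-live.

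The cost is SAP wording, one more model and one table; each unit's start date follows from the randomised order. If the effect is in fact constant, the exposure-averaged interval is wider, by about 1.5 times on a simulation estimate that will vary with the form and average chosen. That cost falls on the companion model only.

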## 2. PARTICIPANTS AND TREATMENT ARMS

Adult patients admitted to hospital during the 12-month study period who had 24-hour exposure to any of the study units will be included if they are not known to be pregnant. Pregnancy status is based on either documented known pregnancy via ObGyn status or BhCG results that are classified as positive using VUMC laboratory cutoffs.

Participants will be in either the control group or the intervention group, depending on when they presented to the hospital, and which hospital unit they were exposed to. Specifically:

- Control Group: Any patient who did not have a 24-hour exposure to a study unit where the intervention was active but did have at least 24-hour exposure to a control unit. The current standard of care in hospitalized patients with reported penicillin allergy is to do nothing, with all care at the discretion of the primary team. Hence, no intervention will be provided.
- Intervention Group: Any patient who had a 24-hour exposure to a study unit at any time where the intervention was active. The intervention includes systematic identification those with a penicillin allergy, application of a penicillin allergy risk stratification tool, and use of an oral amoxicillin test dose challenge order set for patients who stratify as low risk. The risk stratification tool has been demonstrated retrospectively to have a >99% (95% CI 96.4,99.9) negative predictive value for the presence of penicillin allergy in those who stratify as low risk. Test dose challenges with amoxicillin are a recommended part of routine practice in patients who report allergy but have symptoms that are low risk for true or ongoing allergy. When a unit crosses over and becomes a “live” unit with the intervention, a patient who was already admitted on the unit needs to be present for 24 hours afterward to be considered exposed to the intervention.

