### **Analysis of secondary endpoints**

We will proceed with exploring the effect of low-risk penicillin allergy challenge on secondary endpoints in a similar manner as for the primary endpoints:

- i) Endpoints will be described as medians and interquartile ranges or frequencies and proportions
- ii) Binary variables will be compared using an adjusted logistic regression, and ordered or continuous variables will be compared using proportional odds logistic regression
- iii) The odds ratios with confidence will be reported as estimates of effect size.
- iv) Secondary endpoints will be modelled with adjustment for baseline covariates; sensitivity analyses will exclude adjustment and may include imputation for any missing outcomes.
- v) Differential treatment effects will be evaluated using the interaction term, and consequent differential effects reported
- vi) Time to return of penicillin allergy labels will be evaluated using a Cox proportional hazards model with covariate adjustment.

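### The unadjusted sensitivity analyses, as written, drop calendar time, which is confounded with intervention in this stepped wedge

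*SAP*

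**What the plan says.** The primary model in SAP section 10 (Main Analysis) is an "adjusted logistic regression mixed effects model". Its adjustment set opens with time: "the model will be adjusted for the following baseline covariates: time from start of study". Patient factors follow, then "intervention unit as a random effect", and a later sentence adds unit acuity. By the SAP's own label, time is therefore one of the covariates.

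The sensitivity paragraph in the same section says: "We will repeat the main analysis without covariate adjustment". For secondary endpoints, item (iv) of the analysis section says "Secondary endpoints will be modelled with adjustment for baseline covariates" and that "sensitivity analyses will exclude adjustment". Neither place says that time stays in.

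SAP section 2 puts patients in a group "depending on when they presented to the hospital" and according to the unit they were on. Section 8 has 12 units starting in random order at one-month intervals. Units move only from control to intervention.

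**The concern.** Age or sex can be left out of an analysis of randomized units without systematic bias, because randomization balances them in expectation. Calendar time is different. Randomizing the order of the units does not balance time between the arms: the schedule itself puts control experience early and intervention experience late. If time is dropped, any drift in prescribing, documentation or case mix over the year is credited to the intervention.

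A robustness check built this way is hard to read. If it disagrees with the adjusted result, the cause may be drift alone. If it agrees, that may be because bias happened to push the same way.

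The endpoint most exposed is antibiotic utilization. It is the main between-arm secondary endpoint that is not limited to challenged or de-labeled patients, and its use could plausibly drift over a year. The SAP also says that secondary analyses will give weight to effect sizes rather than significance, and in the sensitivity version the effect size is what is biased.

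**Working it through.** **Inputs from the documents.** There are 12 units, one-month steps and a 12-month study (SAP sections 2 and 8). One unit is on intervention from the outset (protocol section 4). There are 10–15 eligible patients per unit-month, and label removal is 0.5% in control against a pessimistic 10% with intervention (SAP section 8).

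**Assumptions.** The documents give no secular trend, no antibiotic rate and no intracluster correlation (ICC). I assume start rates of 10–50%, an ICC of 0.01–0.05, and a trend that is linear in the log odds from month 1 to month 12. The SAP mentions a run-in of unstated length, so one all-control run-in month is shown as an alternative.

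**1. Imbalance in time.** In month t, t units are on intervention and 12 − t are on control.
- Intervention: Σt = 78 unit-months; mean month Σt²/78 = 650/78 = 8.33.
- Control: Σ(12 − t) = 66 unit-months; mean month Σt(12 − t)/66 = 286/66 = 4.33.
- Gap: 8.33 − 4.33 = 4.0 months.
- Within a unit starting in month u (u = 2 to 12), control months average u/2 and intervention months (u + 12)/2, so the gap is 6.0 months.
- With one run-in month the gaps are 4.7 and 6.5 months.

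The correlation of intervention with month is 0.58 overall and 0.71 within unit. Keeping the unit effect alone therefore does not remove the confounding.

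**2. Hand approximation, no true effect.** If the odds change by a factor R over the 11 steps from month 1 to month 12, the spurious odds ratio (OR) is about R^(gap/11).
- Pooled, gap 4: 1.25^(4/11) = 1.08; 1.5^(4/11) = 1.16; 2^(4/11) = 1.29.
- Wholly within unit, gap 6: 1.25^(6/11) = 1.13; 1.5^(6/11) = 1.25; 2^(6/11) = 1.46.

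A random intercept lies between these two.

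**3. Fuller calculation, no true effect.** The pooled column is exact from cell probabilities. The random-intercept columns come from simulation with 12 patients per unit-month: 300 runs per setting for the ORs, 400 for the rejection rates. Ranges run across start rates and ICCs.

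| Trend in odds, months 1–12 | OR, time and unit dropped | OR, time dropped, unit random intercept kept | Rejects OR = 1 at 5%, time dropped, intercept kept |
|---|---|---|---|
| none | 1.00 | 0.99–1.01 | 3–8% |
| 1.25-fold | 1.08–1.09 | 1.10–1.13 | 8–16% |
| 1.5-fold | 1.16 | 1.18–1.24 | 18–46% |
| 2-fold | 1.28–1.29 | 1.33–1.43 | 47–86% |

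Falling trends bias the other way: 0.8-fold gives 0.92 and 0.5-fold gives 0.78 (time and unit dropped). With linear time kept, a 2-fold trend gives 0.98–1.02, and rejection is 4–9% at every trend. Because the simulated trend is itself linear, this shows the model working when the form of time is right.

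**4. Primary endpoint.** The planned OR is (0.10/0.90)/(0.005/0.995) = 22.1. With a 2-fold trend and time dropped, the pooled OR is 28.4. With the random intercept the median is 30–31, against 23–24 with no trend (the latter reflects few control events). The size shifts; the conclusion does not.

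**The case against.** The strongest reply is that no decision rests on these analyses. The conclusion on the main effect comes from the primary model, and the secondary effect estimates come from adjusted models; both contain time. An unadjusted result beside an adjusted one is a common transparency check, and a divergence could itself reveal a trend. The sizes above rest on assumed trends: a doubling of odds within a year at one hospital is large, a 1.25-fold trend gives an OR of only about 1.1, and no trend gives no bias. The rejection rates describe a test to which the SAP attaches no conclusion. The authors may also have meant to drop only patient-level covariates.

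Much of this stands. It confines the problem to the sensitivity results, and the rejection rates only illustrate scale. It does not rescue the wording. Time is named as a covariate, covariate adjustment is removed, and an analyst who follows the text will drop it. Putting time in the primary model already treats drift as possible. A check confounded by design does not test robustness to the patient covariates, because it changes two things at once.

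The unit effect is less clear-cut. The SAP names it as a random effect in a mixed model, so repeating the main analysis may be read as keeping it. For secondary endpoints, "in a similar manner as for the primary endpoints" may carry it over, but the logistic, proportional-odds and Cox models listed there do not name it. That calls for clarification only. Intervals would be too narrow only if unit were left out and outcomes varied by unit.

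**Conclusion.** The concern holds. As written, the sensitivity analyses for the primary and secondary endpoints omit a design term that is correlated with intervention at about 0.6 overall and 0.7 within unit. The 4.0- and 6.0-month gaps follow from the documents' schedule. The bias depends on a trend the documents do not give: with no true effect, ORs of about 1.08–1.13 for a 1.25-fold rise, 1.16–1.24 for 1.5-fold and 1.28–1.43 for 2-fold, spanning unit dropped and unit kept, with the opposite sign for falling trends.

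The primary inference and the main secondary models are unaffected, and the primary sensitivity conclusion would not change at 0.5% against 10%. The practical risk is a misleading sensitivity estimate for antibiotic utilization. It should be fixed, but it does not threaten the trial's main result.

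**What to change.** - In the sensitivity paragraph of SAP section 10 and in item (iv) for secondary endpoints, state that these analyses remove only patient-level covariates and unit acuity. They keep time, in the same form as the primary model, and the unit random effect.
- Present crude proportions by arm as description, without using them as the robustness check.
- Confirm that the between-arm secondary models carry the same unit effect where event numbers allow.

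The cost is SAP wording only. The sensitivity intervals will be somewhat wider, and the sensitivity analysis will no longer be a fully crude comparison; the descriptive proportions serve that purpose.
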